# 2. **Objectives**

There are two primary objectives and seven secondary objectives for this proposal. Primary objectives (i.e., Specific Aims #1 and #2) are:

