## Specific Aim #2: To determine whether adjunctive ketamine is associated with opiate sparing.

This will be measured by documenting each participant's number of Requests for Additional Analgesic Medications (i.e., RAAMs) for acute nociceptive pain during each of the 14 wound care procedures from Day 1 to Day 7 of the Trial.

**The seven secondary outcome measures** of the proposal are: 1) Rates of acute and posttraumatic stress disorder (i.e., ASD and PTSD); 2) Rates of major depressive disorder; 3) Sleep quality and duration; 4) Pain-related anxiety; 5) Catastrophizing; 6) Emotion Regulation and; 7) Trauma resilience.

1) ASD and PTSD will be assessed using the Diagnostic and Statistical Manual of Mental Disorders V-(DSM V). By definition, to meet criteria for PTSD, symptoms must be present for 1 month. As such, prior to the 1-month post-injury time-point, subjects with symptoms consistent with PTSD related to their burn injury will be diagnosed with ASD, rather than PTSD. It is hypothesized that subjects in the K + UC group will have a lower percentage of patients who meet criteria for PTSD, when compared to subjects in the UC group. It is also hypothesized that a number of factors will moderate the presence and severity of ASD and PTSD; these include:

a) Pain, as measured above. Mutual Maintenance Theory: We anticipate that "mean pain" of all 14 sessions (i.e., group average of all observations across all 14 sessions) and the trajectory of pain through the 14 sessions (i.e., group X individual trajectory within session, and, group X individual trajectory across all 14 sessions) will be predictive of PTSD development and PTSD symptom severity at 1-month.

b) Sympathetic reactivity (as measured above). We expect that greater sympathetic reactivity during the wound care procedures will be associated with ASD and PTSD.

c) Depressive symptom severity as measured using the Beck Depression Inventory (BDI-II) during the week of wound care, and at the 1-month time-point.

d) Sleep during the night following wound procedures (measured by both self-report and with the Itamar Watch-PAT200) and at the 1-month time point (self-report).

e) Trauma Resilience (as measured using the Trauma Resilience Scale: Trait- at baseline, and at 1-month time-point).

f) Distress at baseline in reporting the burn event (as measured by self-report and the Itamar Watch-PAT200)

g) Optimism (as measured by the Life Orientation Test: Trait – baseline)

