#### 1. Sample Size Estimate Based on Stay $\geq$ 7 days in Burn ICU.

The sample size calculation is based on the primary statistical procedure for this project which will test the difference in mean pain scores, defined as the average self-report of mean pain score, based on the Numeric Analogue Scale (NAS), during each burn wound care procedures, between individuals randomized to usual care plus placebo (fentanyl plus saline) and those randomized to the intervention arm (usual care + ketamine). PASS Sample Size (Version 14) was used to perform all sample size calculations while considering individuals over the one-year study duration randomized to control and intervention arms in a 1:1 fashion.

In the first case, we further assume that each individual, will, on average, have a length of stay of 7 days thus resulting in 14 wound care procedures performed during hospital stay. We determined the minimum sample size for our trial based on 80% power at p = 0.05 to detect a clinically significant difference in mean pain score during the wound care procedure of 2.0 points between the control and intervention arms with a standard deviation of 3.0. In addition, to account for the clustered nature of procedures performed on individuals, we have used a sample size inflator (also termed "design effect") of 10.1 as described by the Cochrane manual@ conservatively using an interclass correlation of effects of 0.7 amongst repeated measures of pain scores within each individual and 14 observations per individual.

The required sample size needed to accept the alternative hypotheses that the mean pain care score in the intervention arm decreased by 2 points compared to the control arm at the 0.05 level would require 27 individuals per arm (54 total), our anticipated population of 74 eligible individuals is adequate to show a clinically significant improvement for both intervention arms.

@http://handbook.cochrane.org/chapter\_16/16\_3\_4\_approximate\_analyses\_of\_cluster\_randomized\_trials\_for\_a.htm

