#### 2. Corrected Sample Size Estimate for Length of Stay on the Burn ICU $\geq$ 7 days as **estimated on Admission** but, however, where the **Actual Length of Stay on Burn ICU is** $\geq$ **5.5 days** because of Factors that either not present or not evident or were difficult to quantify at time of admission and consent of the patient.

This sample size calculation is based on the primary statistical procedure for this project which will test the difference in mean pain scores, defined as the average self-report of mean pain score, based on the NAS, during each burn wound care procedures, between individuals randomized to usual care (fentanyl plus saline) and those randomized to the intervention arm (usual care + ketamine). PASS Sample Size (Version 14) was used to perform all sample size calculations eligible individuals over the one-year study duration randomized to control and intervention arms in a 1:1 fashion.

In this situation, where Length of Stay is less than the initially estimated >7 days, we further assume that each individual, will, on average, have a length of stay of 5.5 days on the Burn ICU thus resulting in 11 wound care procedures

performed during hospital stay on the Burn ICU. We determined the minimum sample size for our trial based on 80% power at p = 0.05 to detect a clinically significant difference in mean pain score during the wound care procedure of 2.0 between the control and intervention arms with a standard deviation of 4.0. In addition, to account for the clustered nature of procedures performed on individuals, we have used a sample size inflator (also termed "design effect") of 8.0 as described by the Cochrane manual@ conservatively using an interclass correlation of effects of 0.7 amongst repeated measures of pain scores within each individual and 11 observations per individual.

The required sample size needed to accept the alternative hypotheses that the mean pain care score in the intervention arm decreased by 2 points compared to the control arm at the 0.05 level would require 47 eligible individuals (94 total), our anticipated population of 128 eligible individuals is adequate to show a clinically significant improvement for both intervention arms.

@http://handbook.cochrane.org/chapter\_16/16\_3\_4 approximate analyses\_of\_cluster\_randomized\_trials\_for\_a.htm

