# 7. Study Statistics

- a. Primary outcome variable. Described above (Outcomes)
- b. Secondary outcome variables. Described above (Outcomes)
- c. Statistical plan including sample size justification and interim data analysis. Described above

Statistical consultation and initial power estimation were obtained from the Johns Hopkins Biostatistics, Epidemiology, and Database program (BEAD). The Johns Hopkins Institute for Clinical and Translational Research (ICTR) worked with the Ketamine Team to develop the randomization model and the REDCap Database and will continue to serve as consultants throughout the duration of the study. The ICTR expertise will be of particular importance when managing issues such as data cleaning and preparation, preparing interim reports, and in designing and conducting both preliminary and final statistical analyses. Using standard methods, the BEAD suggested that a total sample size of 74-94 participants (n= 37-47 per Condition) should be sufficient to provide a power of .85 to detect a statistically significant difference at p < 0.05. This study team has discussed this issue of power and decided to be conservative and enhance the opportunity of making a definitive statement regarding study objectives and secondary questions. Therefore, the total target sample size will be increased to n= 100. One clarification is important: Funding is for a 1-year period. Should funding end before 94 participants are enrolled the study will have more than sufficient power to address the primary objectives (n=74).

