It is anticipated that the data on Opiate Sparing (i.e., requested additional dose of analgesic medication) will be non-normal and will be analyzed using Mann-Whitney or other nonparametric method as appropriate. Prior to testing hypotheses, univariate distributions of variables will be inspected to assess normality, identify outliers, skewness or other abnormalities in distribution, determine appropriate summaries of location and spread and the need for transformation or nonparametric analysis. Preliminary analyses will determine whether the data meet basic assumptions for parametric tests. If relevant covariates are not balanced by the randomization, or confounds are distributed unevenly across groups, they will be included in the models as covariates. If Opiate Sparing is substantially associated with non-study factors (e.g., age, gender, TBSA) these variables will be statistically controlled as indicated in analyses.

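### Section 7 claims more than sufficient power for both primary objectives at 74 participants, but opiate sparing was never sized, and pain reaches only about 70% on the corrected inputs

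*Combined protocol and SAP*

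**What the plan says.** Section 2 (Objectives) opens: "There are two primary objectives and seven secondary objectives for this proposal". The two primary objectives are Specific Aims #1 and #2. Aim 1 concerns pain. Aim 2 concerns opiate sparing, measured by each participant's number of "Requests for Additional Analgesic Medications (i.e., RAAMs) for acute nociceptive pain during each of the 14 wound care procedures".

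The sample-size text has two parts. The one for a 7-day stay begins: "The sample size calculation is based on the primary statistical procedure for this project which will test the difference in mean pain scores". The corrected one for a 5.5-day stay begins: "This sample size calculation is based on the primary statistical procedure for this project which will test the difference in mean pain scores". Both are set at 80% power and p = 0.05, and they give 27 per arm (54 total) and 47 per arm (94 total).

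The Data Analysis Plan expects the opiate-sparing data to be unsuitable for ANCOVA. It says that they "will be non-normal and will be analyzed using Mann-Whitney or other nonparametric method as appropriate".

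Section 7 then cites a power of .85 for 74-94 participants and raises the target to 100. It adds, for the case in which the one-year funding runs out: "Should funding end before 94 participants are enrolled the study will have more than sufficient power to address the primary objectives (n=74".

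**The concern.** The statement in section 7 covers the primary objectives in the plural, yet the calculations behind it concern one endpoint. A sample size that suits a mean pain score says nothing about a count of requests. That count has its own rate, spread and plausible reduction, and is tested by a different method. If Aim 2 was never sized, its stated power has no basis.

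There is a second difficulty. The protocol revised its own inputs (SD 4.0 instead of 3.0, 11 sessions instead of 14) and arrived at 94 participants. Calling 74 more than sufficient returns to the inputs that the correction replaced.

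The sentence is also what reassures a reader if enrolment ends at 74. A non-significant comparison of requests could then be taken for the result of an adequately powered primary test.

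**Working it through.** **Step 1: reproduce the printed sizes.** The inputs come from the two sample-size subsections: difference 2.0, ICC 0.7, 80% power, alpha 0.05 and 1:1 allocation, with SD 3.0 and 14 sessions in the first and SD 4.0 and 11 sessions in the second. Sidedness is not stated. Two-sided reproduces the printed sizes; one-sided does not (about 21 and 37 per arm).

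Design effect = 1 + (m − 1) × ICC:
- 7-day: 1 + 13 × 0.7 = 10.1
- 5.5-day: 1 + 10 × 0.7 = 8.0

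The unclustered two-sample t-test size is multiplied by design effect / m:
- 7-day: 36.3, rounded up to 37; 37 × 10.1/14 = 26.7, so 27 per arm
- 5.5-day: 63.8, rounded up to 64; 64 × 8.0/11 = 46.5, so 47 per arm

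Both printed sizes are reproduced. The formula is a two-sample comparison of participant-mean NAS. Nothing about requests enters it.

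**Step 2: Aim 1 power at the stated totals.** The SD of a participant's mean is SD × √(design effect / m):
- 7-day: 3.0 × √(10.1/14) = 2.55
- 5.5-day: 4.0 × √(8.0/11) = 3.41

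Two-sided t-test power for a difference of 2.0:

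| Total (per arm) | 7-day inputs | 5.5-day inputs |
|---|---|---|
| 74 (37) | 91% | 70% |
| 94 (47) | 96% | 80% |
| 100 (50) | 97% | 83% |

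At 74 and 94, none of these figures is the .85 in section 7. At 74, only the 7-day inputs pass 80%.

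**Step 3: what the documents give for Aim 2.** They give the endpoint (number of requests), a provisional test, and the expectation of non-normality. They give no control-arm rate, no spread and no expected reduction. Power needs all three, so it cannot be computed from the documents.

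**Step 4: how far an assumed answer can move.** Everything in this step rests on assumptions that are not in the documents. All figures are for 37 per arm with a two-sided Mann-Whitney test at 0.05.

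*Requests derived from pain.* Session NAS is simulated with SD 4.0, ICC 0.7 and 11 sessions, then rounded and bounded to 0-10. At most one request is counted per session, when NAS is 7 or more. The control mean is 4-8 (5-7 for the uniform-acceptance case).
- Difference of 2.0 before bounding, every offer accepted: about 56-65%. Bounding shrinks the realised NAS difference to about 1.5 points.
- Same, but willingness to accept varies uniformly from 0 to 1 between participants: about 40%.
- Realised NAS difference restored to 2.0, every offer accepted: about 82-90%.

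*Request totals simulated directly* as negative binomial, with control mean 3-22 per participant and dispersion parameter 0.5-5:
- Requests halved: about 31% to over 99%.
- Requests reduced by 30%: about 12% to 81%.

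**The case against.** The strongest reply is that the omission should not be turned into a number. A reader might infer that the corrected inputs put Aim 2 at roughly 56-64% power at 74, so that the test misses a real effect in about four trials of ten. The documents do not support this. The corrected inputs describe pain scores, not requests. The threshold model that yields such figures tests a realised difference of about 1.5 points instead of the planned 2.0. It also departs from the protocol's PRN text, which assesses need before, during and after wound care, allows more than one dose per session, has a second trigger based on a rise in pain, and adds nursing judgement. Restoring the 2.0 difference alone moves the answer above 80%. By the same token, the claim for Aim 2 cannot be said to hold only under SD 3.0. This part of the reply stands in full.

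Three further points are fair. The test for Aim 2 is not fixed, since the plan allows another nonparametric method and covariate adjustment. The target is 100, and 74 is a fallback if funding ends, not a rule for stopping accrual. And no section says that a non-significant request result would be read as absence of opiate sparing; that is a risk of interpretation, not a stated intention.

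None of this rescues the sentence in section 7. If power for Aim 2 can fall almost anywhere, it cannot be declared more than sufficient. Nor does the reply touch Aim 1, where the shortfall follows from the protocol's own inputs.

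**Conclusion.** The point holds. For Aim 2 the power claim is unsupported: the endpoint was never sized and its power is unknown. That is not a finding that Aim 2 is underpowered. Plausible models fall on both sides of 80%, and the figures in step 4 show only how strongly the answer depends on assumptions.

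For Aim 1 the claim depends on which inputs are used: about 91% at 74 on the 7-day inputs, but about 70% on the corrected inputs, which is below the planned 80% and the .85 in section 7. These Aim 1 figures assume a two-sided test, equal arms, the stated ICC and no loss to dropout. The sample-size arithmetic itself is sound; the error lies in how far section 7 extends it.

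**What to change.** In section 7:
- Limit the power statement to Aim 1 (mean NAS) and give it for both input sets: about 91% (7-day) and 70% (5.5-day) at 74; about 96% and 80% at 94.
- Delete the sentence saying that 74 is more than sufficient for the primary objectives.
- State that Aim 2 was not sized. Alternatively, give its power as a range under declared assumptions about the request rate, its spread between participants and the reduction sought, for the test that will be used. The illustrative percentages above should not be copied into the protocol as the Aim 2 power.
- Commit to reporting Aim 2 as an estimated difference with a confidence interval, and state that a non-significant result will not be read as absence of opiate sparing.

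The cost is a few sentences, plus a short simulation if a range is given. No participants or procedures are added. The downside is a less favourable stated power.

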# Data Analysis Plan

[name], a professional biostatistician from the JH BEAD program specializing in clinical trials and longitudinal data analysis, had assisted Drs. [name] and [name] in conducting the statistical analyses in consultation with Going forward, this role will be assumed by biostatisticians at the JHU-ICTR.

The primary data analyses (Pain variables) will be conducted using analysis of covariance, or, longitudinal growth modeling (if normality assumptions are met) to examine group differences both in cross-section and longitudinally. If normality assumptions are violated then appropriate nonparametric tests will be utilized (e.g., Wald statistic). These methods allow for statistical controlling multiple potential confounding baseline variables and are robust against dropout - expected to be minimal. Data from the following study were used to generate this power estimate (Beaudoin, 2014).

Prior to study start-up, it is anticipated that, since ANCOVA is the recommended procedure for analyzing pre- to post- treatment change scores, that is the test that will be utilized for the primary aim, because: it is more powerful than t-test and Mann-Whitney; it can adjust for baseline group differences; it can be adjusted for baseline randomization strata; and, it can be utilized in analyzing repeated measures such as in the present study.

Prior to testing hypotheses, univariate distributions of variables will be inspected to assess normality, identify outliers, skewness or other abnormalities in distribution, determine appropriate summaries of location and spread and the need for transformation or nonparametric analysis. Preliminary analyses will determine whether the data meet basic assumptions for parametric tests. If relevant covariates are not balanced by the randomization, or confounds are distributed unevenly across groups, they will be included in the models as covariates.

If Pain Intensity is substantially associated with non-study factors (e.g., age, gender, TBSA) these variables will be statistically controlled as indicated in analyses.

The data on average (or summed) Opiate Sparing Effects from baseline to post-treatment, and within group and between group changes over time are likely not to meet criteria for parametric analysis, that is, they are expected to be non-normally distributed and thus inappropriate for Analysis of Covariance (ANCOVA).

It is anticipated that the data on Opiate Sparing (i.e., requested additional dose of analgesic medication) will be non-normal and will be analyzed using Mann-Whitney or other nonparametric method as appropriate. Prior to testing hypotheses, univariate distributions of variables will be inspected to assess normality, identify outliers, skewness or other abnormalities in distribution, determine appropriate summaries of location and spread and the need for transformation or nonparametric analysis. Preliminary analyses will determine whether the data meet basic assumptions for parametric tests. If relevant covariates are not balanced by the randomization, or confounds are distributed unevenly across groups, they will be included in the models as covariates. If Opiate Sparing is substantially associated with non-study factors (e.g., age, gender, TBSA) these variables will be statistically controlled as indicated in analyses.

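### The primary pain test is chosen by an undefined normality check on the outcome data, with an unnamed fallback; one baseline-adjusted model should be primary whatever the distribution

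*Combined protocol and SAP*

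**What the plan says.** All of this is in section 7, Study Statistics, under Data Analysis Plan.

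- **Primary pain method:** analysis of covariance, or "longitudinal growth modeling (if normality assumptions are met").
- **Fallback:** "If normality assumptions are violated then appropriate nonparametric tests will be utilized (e.g., Wald statistic"). No other method is named for pain.
- **Covariates:** the next sentence reads "These methods allow for statistical controlling multiple potential confounding baseline variables".
- **Preferred test:** the following paragraph expects ANCOVA for the primary aim, because "it is more powerful than t-test and Mann-Whitney; it can adjust for baseline group differences".
- **Trigger:** before hypothesis testing, "univariate distributions of variables will be inspected to assess normality", along with outliers, skewness and "the need for transformation or nonparametric analysis". Then: "Preliminary analyses will determine whether the data meet basic assumptions for parametric tests". No test, cut-off or residual check is given.

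Mann-Whitney is assigned to opiate sparing, not to pain. The sample size sections (section 4) size the trial on a 2.0-point difference in mean NAS and use no baseline adjustment.

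**The concern.** Three things are wrong with the rule itself.

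1. The primary test is settled only after the outcome distributions have been seen, by a judgement with no stated criterion.
2. The check looks at the variables. ANCOVA does not need normal raw scores; what matters is the behaviour of the residuals and of the treatment estimate.
3. The destination is undefined. A Wald statistic is an estimate divided by its standard error (or the multivariate version of that). It can come from the parametric or mixed model being set aside, or from a rank-based model, so naming it does not tell the analyst what to run.

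If the analyst lands on an unadjusted rank test, the trial may lose baseline adjustment and an estimate on the 2.0-point scale for which it was sized.

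**Working it through.** **Inputs from the plan** (Corrected Sample Size Estimate): difference 2.0, SD 4.0, ICC 0.7, 11 sessions, 80% power, p = 0.05 (two-sided assumed), 47 per arm. The seven-day case uses SD 3.0, 14 sessions and 27 per arm. **Assumed, because not given:** baseline-outcome correlation ρ, shown over a range.

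**Step 1. Reproduce the plan's sample sizes.** Design effect = 1 + (m - 1) × ICC; n per arm = (t-test n) × design effect / m.
- SD 4: 1 + 10 × 0.7 = 8.0; 64 × 8.0/11 = 46.5, so 47. This matches.
- SD 3: 1 + 13 × 0.7 = 10.1; 37 × 10.1/14 = 26.7, so 27. This matches.

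**Step 2. Power under each possible test** (47 per arm, SD 4.0).
- SD of a patient mean = 4 × √(8.0/11) = 3.41; standardised difference = 2/3.41 = 0.586.
- Unadjusted comparison: Φ(0.586 × √(47/2) - 1.96) = Φ(0.88) = 81.1% (80.3% by exact t).
- Unadjusted Mann-Whitney, relative efficiency 3/π = 0.955: effective n = 44.9, power 79.3%. Loss against the unadjusted comparison: 81.1 - 79.3 = 1.8 points.
- ANCOVA: replace 3.41 by 3.41 × √(1 - ρ²).

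| Assumed ρ | ANCOVA | Gap to Mann-Whitney, formula | Gap, simulation (normal data) |
|---|---|---|---|
| 0.3 | 84.6% | 5.3 | 4.7 |
| 0.4 | 87.3% | 8.0 | 7.8 |
| 0.5 | 90.7% | 11.4 | 10.5 |
| 0.6 | 94.4% | 15.1 | 15.6 |

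The gap is 1.8 points at ρ = 0. At 37 per arm, ρ = 0.3-0.6 gives 3-8 points with SD 3 and 6-19 points with SD 4. In simulation on bounded scores, a rank ANCOVA that keeps the baseline came within about 1.5 points of ordinary ANCOVA.

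**Step 3. Would the check fail?** An SD of 4.0 is very wide for a 0-10 scale: a uniform distribution on 0-10 has SD 10/√12 = 2.9. Scores were simulated, rounded and cut off at 0 and 10, with 47 per arm, control mean 6 or 7, a 2-point effect and ρ of 0.3, 0.5 or 0.6. The share of trials failing Shapiro-Wilk at 5% was:

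| Quantity checked | SD 4 | SD 3 | SD 2-2.5 |
|---|---|---|---|
| Patient means | 92-98% | 33-65% | 4-31% |
| ANCOVA residuals | 7-47% | 6-18% | not needed here |

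Single-session integer ratings failed in 78-100% of trials across all these SDs. Shapiro-Wilk stands in here for the plan's undefined inspection.

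**Step 4. Is the switch needed?** With no treatment effect, SD 4, control mean 6 and ρ = 0.5, ANCOVA rejected in 4.6% of 2,000 simulated trials (Monte Carlo standard error √(0.05 × 0.95/2000) = 0.5 points). Patient means failed Shapiro-Wilk in 95% of those same trials. A separate simulation of bounded patient means with robust standard errors gave 3.7-5.5%.

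**The case against.** The strongest reply is that the plan never says what the larger power figures require.

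- **The fallback is not Mann-Whitney.** A reader might infer that pain would move to a test the plan itself ranks below ANCOVA, since "it is more powerful than t-test and Mann-Whitney" stands close by. That joins two separate statements. The documents give Mann-Whitney to opiate sparing and leave the pain fallback unnamed.
- **Baseline adjustment is not stated to be lost.** The sentence after the fallback says the methods allow control of baseline variables, and later sentences add imbalanced or associated covariates to the models. If the fallback keeps covariates, the power cost is near zero. Loss of adjustment is a risk of the vague wording, not a stated consequence.
- **The 5-16 points are mostly a gain forgone.** The trial was sized without baseline adjustment, so against the planned 80% the loss is about 2 points.
- **The switch need not fire.** The tested variable is a patient mean, not a single integer rating. At smaller SDs most trials would pass, and transformation is also allowed.

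All four stand, and they limit the size of the problem. They do not rescue the rule: it remains undefined in its trigger and its destination, it looks at raw distributions, and transformation adds another choice made from the data. The type I error of the two-stage procedure was not estimated, so no inflation is claimed.

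**Conclusion.** The point holds as a defect in how the primary pain analysis is specified. The test depends on an undefined look at the outcome data, aimed at the wrong quantity, with a fallback that the text does not identify. At the plan's own SD of 4.0 the check would probably fail if applied to patient means, yet ANCOVA holds its type I error there, so the switch buys no protection.

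The cost is conditional: nearly nothing if the fallback keeps covariates; about 2 points of power against the planned 80% if it is an unadjusted rank test; about 5-16 points against baseline-adjusted ANCOVA at 47 per arm, SD 4 and an assumed ρ of 0.3-0.6. The documents do not support a reading that the trial will lose that power, or that the switch will almost always occur whatever the SD.

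**What to change.** For the pain outcome, delete the normality-triggered switch and the reference to the Wald statistic. State instead that:

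1. one baseline-adjusted mean model of NAS is primary whatever the shape of the distribution, with the model and the baseline rating named in advance;
2. standard errors are patient-level robust (sandwich) or from a patient-level bootstrap;
3. the result is reported as a mean difference with a 95% CI, on the scale of the 2.0-point target;
4. a baseline-adjusted rank ANCOVA is a sensitivity analysis.

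Distributions can still be described, but should not select the primary test. The cost is a few sentences of plan wording, with no new data and no extra patients.
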